Falls. We will follow the STURDY screening protocol to identify falls in this study. According to STURDY, a fall is defined as any fall, slip, or trip, in which the participant loses his or her balance and lands on the floor, ground, or at a lower level. Following the BV, we will ask participants to document any incidence of a fall on their compliance calendar at the end of each day or the morning of each subsequent day. Participants will be instructed to contact the research coordinator after any fall (after seeking medical attention, if needed).

A standardized follow-up interview will be administered to obtain details about when the fall occurred, the circumstances of the fall, and any resulting injuries and treatment. If a previously

unreported fall is reported during a follow-up interview, a second fall follow-up interview will be administered.

Cognition. Cognitive performance will be measured using the standard Cogstate Brief Battery. The Cogstate Brief Battery measures four core cognitive domains including processing speed, attention, visual learning, and working memory. Participants will complete the Brief Battery at the BV and the FV. The assessment will be administered on a standard PC laptop in a quiet, private room.

The Cogstate Brief Battery has been used extensively in research as a rapid and reliable screening assessment in a range of clinical indications. It has also been widely used in the context of measuring cognitive dysfunction relative to healthy groups in adult populations. Each of the tests maintains high reliability across repeated testing and cross-sectional research designs.

Other data collected:

Medical history. A brief prescreening questionnaire will be administered to collect general medical history information and specifically information related to the inclusion and exclusion criteria. This will be administered by telephone or in-person. Information will be confirmed at the SV.

Contact information. Detailed contact information for the participant and an emergency contact will be obtained at the PSV. Contact information will be updated at subsequent visits, if necessary.

Demographics. At the SV, detailed demographic information will be collected.

Vital Signs. Seated blood pressure measurement and heart rate will be recorded at the SV. This is to partially determine eligibility. A systolic blood pressure >200 mm Hg will exclude participation.

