Taste test. Participants will be asked to taste a sample of each study fruit at the SV to ensure palatability. Responses will be recorded to document participant agreement to comply with either assignment at randomization.

Anthropometrics. Height will be measured at the BV using a floor stadiometer. Weight will be obtained at the BV and the FV using a digital calibrated scale.

Medications. Participants will provide a list of their current medications at the BV, which will be updated at the FV, if necessary.

Sleep. The Pittsburgh Sleep Quality Index will be administered at the BV and the FV. Participants can complete this questionnaire on their own, but it will be reviewed for

completeness and entered by study staff. The PSQI is a self-rated questionnaire which assesses sleep quality and disturbances over a 1-month time interval. Measures include subjective sleep quality, sleep latency, sleep duration, habitual sleep efficiency, sleep disturbances, use of sleeping medication, and daytime dysfunction. The sum of scores yields one global score. It has been shown to be consistent, valid, sensitive, and specific in distinguishing good and poor sleepers in research settings.

Incontinence. The Questionnaire for Urinary Incontinence Diagnosis will be given at the BV and the FV. QUID is a self-administered, 6-item questionnaire used to distinguish between stress urinary incontinence and urge urinary incontinence. It is a reliable and valid diagnosing tool for incontinence when compared to standard clinical evaluation in an outpatient setting.

Dietary Intake. The NHANES 2009-10 Dietary Screener Questionnaire (DSQ) will be given at the BV and the FV. It is a self-administered questionnaire, which asks about the frequency of consumption in the past month of selected foods and drinks. The DSQ captures intakes of fruits and vegetables, dairy/calcium, added sugars, whole grains/fiber, red meat, and processed meat.

Quality of Life. The CDC Health-Related Quality of Life Measures will be administered to participants at the BV and the FV. The HRQOL includes 4 self-reported questions related to overall health, physical health, mental health, and their effects on day-to-day living.

Cardiac ectopy. Atrial and ventricular premature beats will be detected by a 24-hour Holter monitor. Holter monitors will be fitted to participants at the BV and the FV and worn for at least 24-hours before returning them for data upload.

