Specimen collection. Participants will undergo 8-hour fasting blood draws and spot urine collections prior to their BV and their FV. Collections will occur at the CRC by a registered nurse. A total of 45 mL of blood will be taken at both the BV and the FV. Approximately 30 mL of urine will also be collected at each visit. The CRC will process and aliquot serum, plasma, whole blood and spot urine samples. Samples will be stored at -80°C in BIDMC freezers. Following the conclusion of the trial, all samples from BV and FV will be sent to Quest Diagnostics, a CLIA-certified laboratory for analysis. For each participant's BV and FV samples, laboratory testing will include C-terminal telopeptide of type I collagen, troponin I, total and HDL-cholesterol, AST, ALT, albumin, total and direct bilirubin, creatinine, albuminuria, fasting glucose and insulin, fructosamine, free fatty acids, C-reactive protein, and white blood cell count.

For immune diversity measurement, 3-5 mL of freshly spun specimens will be transported from the CRC at baseline and at the end of 12 weeks of intervention to the laboratory of collaborator [name], PhD. In addition to conducting high-throughput AIRR-seq at low cost, his laboratory has developed new computational methods to assess the overall diversity of the 40,000+ sequences measured in a given blood sample, along with cutting-edge methods for measuring the overlap between repertoires. His laboratory will perform AIRR-seq as previously described, sequencing every measureable component of the immune repertoire (~40,000

sequences for each participant at each time point – approximately 3.7 million sequences) and will provide multiple calculated measures of diversity on each individual at each time point, including species richness and entropy.

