- Performance monitoring with feedback – tracking enrollment and follow-up (observed/expected, overall and by key subgroups); monitoring missed visits, data completeness, protocol deviations, and data entry errors; distributing feedback through routine trial monitoring reports for the investigators, safety monitor, and IRB as needed. These reports, together with constructive feedback, have an important role in identifying and resolving issues expeditiously.

9. Randomization and Masking

Randomization

Random treatment assignment will be generated via a web-based system available to the research staff. Allocation uses centrally-allocated 1:1 permuted block randomization in blocks of 2 and 4. Eligibility and baseline data will be collected and entered into the database. The system will confirm eligibility and assign the study fruit.

Masking

Because this is a whole foods study, it is not feasible for treatment assignments to be masked to the participants or the research coordinator. Clinicians conducting ABPM and Holter readings and laboratory technicians will be blinded to study groups.

10. Intervention and Control Arms

This trial uses a pragmatic design to maximize generalizability and adherence. Participants randomized to the blueberry arm consume the equivalent of 1 cup of fresh blueberries daily in the form of frozen whole blueberries for 12 weeks. Blueberries are provided in a single-batch from the U.S. Highbush Blueberry Council. All participants have freezers in their apartments to store a supply of blueberries. Surplus storage will be kept in a freezer in the main kitchen for subsequent pick-ups at week 4 and week 8 after randomization.

Those in the control arm are asked to consume no blueberries and to consume an isocaloric portion of dried dates, equivalent to 2 dates daily for 12 weeks. All dates will be pitted and purchased from the same supplier. Dates are an ideal control because they have similar amounts of fiber, potassium, and calories compared to blueberries. The USDA estimates that dates contain approximately 1.6 mg of total polyphenols per 100 gm of edible content (~3 dates). By contrast, blueberries contain approximately 100 mg or more. Therefore, we expect a substantial anthocyanin difference between arms.

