SBP >200	Notify PI and advise participant to follow-up with PCP within 1 day (refer to emergency room if symptomatic)
SBP >180	Notify PI and advise participant to follow-up with PCP within 3 days (same day if symptomatic)
SBP >160, ≤180	Advise participant to follow-up with PCP within 1 month
DPB >120	Notify PI and advise participant to follow-up with PCP within 1 day (refer to emergency room if symptomatic)
DBP >110	Notify PI and advise participant to follow-up with PCP within 3 days (same day if symptomatic)
DBP >100, ≤110	Advise participant to follow-up with PCP within 1 month
Pulse >120 bpm	Do not have participant participate in the SPPB and advise them to follow-up with their PCP within 7 days
SBP <90	Notify PI and advise participant to follow-up with PCP within 7 days
DBP <40	Advise participant to follow-up with PCP within 1 month

Table 4. ABPM daytime average alert values.

Issue	Action
SBP <90	Notify PI and advise participant to follow-up with PCP within 2 weeks
DBP <50	Notify PI and advise participant to follow-up with PCP within 2 weeks
SPB 130-149	Notify PI and advise participant to follow-up with PCP within 2 months
DBP 80-89	Notify PI and advise participant to follow-up with PCP within 2 months
SBP 150-174	Notify PI and advise participant to follow-up with PCP within 1 month

DBP 90-104	Notify PI and advise participant to follow-up with PCP within 1 month
SBP 175-194	Notify PI and advise participant with follow-up with PCP within 1 week
DBP 105-114	Notify PI and advise participant to follow-up with PCP within 1 week
SBP \geq 195	Notify PI and call participant immediately to advise them to follow-up with PCP within 1 day (go to emergency room if symptomatic)
DBP \geq 115	Notify PI and call participant immediately to advise them to follow-up with PCP within 1 day (go to emergency room if symptomatic)

Participants that undergo the fasting blood draw will receive their results, along with standard ranges for interpretation, at the end of the study with two exceptions. A Comprehensive Metabolic Panel (CMP) and a Complete Blood Count (CBC) will be run in real-time and participants will receive those results once they are available. The PI will review all CMPs and CBCs at baseline and follow-up within 1 day as a safety check. Participants will be notified via phone of any results that require immediate medical attention.

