Although the duration of the study is relatively short, the older study population increases the likelihood of medical events occurring unrelated to participation in this trial.

All serious adverse events and all unanticipated problems will be reported individually to [name] and the study PI within 7 days of when the research coordinator learned of the event.

In general, all other adverse events will be reported in aggregate form to the study PI and independent safety monitor at the time of regular data reports.

12. Analysis

Experimental design

We will conduct a single-center, randomized, parallel-design trial comparing whole frozen blueberries to an isocaloric serving of dried dates, with single-blind assessment of outcomes among 70 adults aged 70 years and older.

Analysis plan

The trial statistician will conduct all analysis of study data. Working with the PI, the statistician will develop an appropriate analysis plan. Our analyses will be conducted using the intention-to-treat principle, with linear regression models that adjust for baseline values as our primary statistical method.(41) If missing data exist (e.g., due to attrition), linear mixed models that incorporate both baseline and end-of-treatment values will be used. Because randomization in studies of this size can be imperfect, we will also adjust for any baseline characteristics that appear to be uneven (typically at $p < 0.10$). Because of the strong underlying hypotheses and correlated nature of our outcomes, we do not intent to adjust for multiple comparisons, but will treat results that are not corroborated by related outcomes with caution. Methods appropriate for clustered data (e.g., generalized estimating equations) will be used if multiple household members are recruited.

Power and sample size

We estimate power for our continuous endpoints, contrasting end-of-treatment values between arms (using $N=70$). With $\alpha=0.05$ and power=80%, we can detect a 0.68 standardized effect size. This is considered a medium-to-large-sized effect, similar to that tested in many studies of blueberries. With power=50% (i.e., aiming for an exact p -value=0.05), we can detect a 0.48 standardized effect size (medium). Thus, we should detect most moderate-to-large and many medium-sized effects. Thus, we should detect most moderate-to-large and many medium-sized effects.

13. Data Management

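### Section 12 adds covariates to the model because they look unbalanced at about p < 0.10, and does not say whether that model is the primary one

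*Protocol*

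**What the plan says.** The analysis plan in protocol section 12 names "linear regression models that adjust for baseline values as our primary statistical method", under intention to treat. It then gives the imperfection of randomisation at this sample size as the reason for a second step: "we will also adjust for any baseline characteristics that appear to be uneven (typically at" p < 0.10). No candidate characteristics are listed. The threshold is described as typical, not fixed. The further adjustment is not ranked as part of the primary model or as supplementary to it.

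Four other places bear on the point:

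- **Section 9, Randomization:** "Allocation uses centrally-allocated 1:1 permuted block randomization in blocks of 2 and 4". No stratification factors are named.
- **Section 12, Power and sample size:** with 70 participants and 80% power, "we can detect a 0.68 standardized effect size". At 50% power the figure is 0.48.
- **Section 7, Specimen collection:** "Following the conclusion of the trial, all samples from BV and FV will be sent to Quest Diagnostics". Section 11 makes an exception: "A Comprehensive Metabolic Panel (CMP) and a Complete Blood Count (CBC) will be run in real-time".
- **Section 7, Demographics and Medications:** "At the SV, detailed demographic information will be collected", and "Participants will provide a list of their current medications at the BV". Obvious predictors are therefore in hand before randomisation.

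**The concern.** Under central 1:1 randomisation a baseline difference between arms is a chance event. A significance test on it says nothing about whether the characteristic predicts blood pressure, physical performance or cognition. A strong predictor that happens to be balanced is left out, although adjusting for it would sharpen the estimate. An irrelevant variable that happens to be unbalanced goes in. It then costs precision, because it is correlated with treatment in that sample.

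The selection is made after arm-level data have been seen. For laboratory values outside the two real-time panels it can be made only when the follow-up results also exist, because both sets of samples are assayed together after the trial ends. With an open candidate list, a soft threshold and no stated rank for the second model, the final model is unknown until late. A reader cannot tell which of two results is the main one.

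**Working it through.** **Inputs from the protocol.** N = 70, taken as 35 per arm under 1:1; alpha 0.05; effects of 0.68 and 0.48 SD; selection at p < 0.10.

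**Assumptions not in the protocol.** K = 10 or 20 candidate covariates; correlation r = 0.5 between baseline and final outcome; normal data; no dropout; no household clustering. Three of the candidates form the fixed set. Their coefficients are 0, 0, 0 (none); 0.15, 0.15, 0.10 (weak); or 0.3, 0.2, 0 (moderate). With independent candidates they add this much outcome variance beyond baseline:

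- weak: 0.0225 + 0.0225 + 0.01 = 5.5%
- moderate: 0.09 + 0.04 = 13%

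**Step 1: the plan's own figures.** For a two-sided two-sample t-test the noncentrality is d × √(n/2) with n = 35.

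- d = 0.68: 0.68 × √17.5 = 2.84, power 80.1% (stated 80%)
- d = 0.48: 0.48 × √17.5 = 2.01, power 50.8% (stated 50%)

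Both reproduce. They contrast final values only. Adjusting for baseline at r = 0.5 cuts the residual SD to √(1 − 0.25) = 0.866, which is why the powers below are higher.

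**Step 2: how often the rule acts.** With independent candidates, the expected number flagged is 0.10 × K and the chance of at least one is 1 − 0.9^K.

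- K = 10: 1.0 expected, 65%
- K = 20: 2.0 expected, 88%

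**Step 3: power of three models.** There were 10,000 simulated trials per setting. Each candidate was t-tested at 0.10 and added to the model if flagged. Entries are power in %: baseline only / rule / baseline plus the fixed three.

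| Covariates | K | 0.48 SD | 0.68 SD |
|---|---|---|---|
| none | 10 | 61.7 / 59.4 / 60.1 | 89.3 / 87.4 / 87.8 |
| none | 20 | 62.6 / 57.3 / 60.6 | 89.6 / 85.7 / 88.3 |
| weak | 10 | 61.1 / 58.7 / 62.6 | 89.1 / 87.8 / 90.1 |
| weak | 20 | 61.1 / 56.2 / 61.9 | 89.0 / 85.1 / 90.1 |
| moderate | 10 | 61.7 / 60.3 / 68.1 | 89.0 / 88.5 / 93.0 |
| moderate | 20 | 62.1 / 57.7 / 68.3 | 89.6 / 86.2 / 93.1 |

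The Monte Carlo standard error is about 0.5 points at 0.48 SD and 0.3 at 0.68 SD.

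- Rule against baseline only: loses 1.4 to 5.3 points at 0.48 SD and 0.5 to 3.9 at 0.68 SD.
- Rule against the fixed set, at 0.48 and 0.68 SD respectively: none 0.7–3.3 and 0.4–2.6; weak 3.9–5.7 and 2.3–5.0; moderate 7.8–10.6 and 4.5–6.9.

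**Step 4: sensitivity.**

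- Candidates correlated 0.3: at least one is flagged in 58–59% (K = 10) or 79–80% (K = 20) of trials. The rule runs from 0.2 points above baseline-only to 3.5 below. It trails the fixed set by 0.5–1.7 (none), 2.8–5.6 (weak) and 4.7–10.2 (moderate). Here the same coefficients add 8.7% (weak) and 16.6% (moderate) of variance.
- r = 0.7, independent candidates: the rule trails the fixed set by 0.4–3.5, 1.3–6.7 and 2.0–12.9.
- A separate simulation (8,000 trials, r = 0.6, effect 0.5 SD, 15 candidates) gave baseline only 72%, rule 70% and fixed set 86% when three covariates explained 20% of the variance. With no prognostic covariate, baseline-only gave 73% and the rule 68%.

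**Step 5: validity.** Over 18 null settings the rule's type I error was 3.7–5.3%, and the mean estimate lay within 0.006 SD of zero. In the separate simulation it fell to 3.4% when covariates explained 30% of the variance, so the rule becomes conservative. If the more favourable of the baseline-only and rule-adjusted results were reported, type I error there was 6.0–6.8%.

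**The case against.** The case for leaving the text alone has five parts.

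1. **The primary method is named first.** The sentence on uneven characteristics follows it, so the natural reading is that it is supplementary. Ranking models and listing covariates is ordinary work for a statistical analysis plan, and section 12 says one will be developed. This has some force: the missing rank alone would be a wording point. But the protocol does more than leave the matter open. It commits to a selection rule, and an analysis plan faithful to it would inherit that rule.
2. **Validity is not harmed.** This stands in full. At r = 0.5 with independent candidates the rule still has 85–90% power at 0.68 SD and 56–62% at 0.48 SD, above the stated 80% and 50%.
3. **The losses rest on assumptions.** This also stands. The largest gaps give the fixed set the truly prognostic covariates. In the weak independent case at 0.48 SD the fixed set beats baseline-only by just 0.8–1.5 points, about what it would cost if the covariates were useless. That is an argument for baseline-only adjustment as an acceptable alternative. It does not support the rule, which does no better than baseline-only in nearly every setting.
4. **Not every imbalance is pure chance.** Under section 10 a second household member takes the first member's fruit without being randomised, so that person's arm is known before enrolment. This is a fair caveat, and clustering would also shift the flag rates. It does not make a p-value a sensible way to choose covariates.
5. **Most candidates are known by baseline.** Demographics, medications, blood pressure and function are, so the timing point is confined to laboratory values. The protocol does not list what the two real-time panels contain, so the exact share assayed late cannot be counted.

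**Conclusion.** The concern holds. The protocol fixes a rule that chooses covariates by chance imbalance, with an open candidate list and a soft threshold, and does not rank the resulting model against the named primary method. It should be fixed, but it is not a threat to validity: no bias, no type I inflation when applied mechanically, and no danger to the stated detectable effects.

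The rule brings essentially no power gain over adjusting for baseline alone and can lose about 5 points. Its shortfall against covariates fixed in advance runs from under 1 point when they are useless to about 10 when they are moderately prognostic, at r = 0.5. These sizes depend on the assumed number of candidates, r and covariate strength. The direction was stable across the settings tried, apart from two correlated-candidate settings in which the rule was 0.2 points ahead of baseline-only, within simulation error. Type I error rises to about 6–7% only if the better of two unranked results were reported, which the protocol does not propose but does not rule out.

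**What to change.** In section 12, replace the sentence on uneven characteristics. State that the primary model adjusts for the outcome's baseline value plus a small set of covariates already collected and fixed before any arm-level data are seen. Age and sex would be natural choices, with baseline antihypertensive use added for the blood pressure outcomes. If no covariate is trusted to be prognostic, state that the primary model uses the baseline value alone. Keep any adjustment prompted by observed imbalance only as a labelled sensitivity analysis. The covariate set itself can be named in the statistical analysis plan.

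The cost is one or two sentences and no new data or participants. Three extra covariates take the residual degrees of freedom from 67 (70 − 3) to 64. If none is prognostic, the simulations put the loss at 1.3–2.0 power points against baseline-only adjustment, for example 61.7% to 60.1% at 0.48 SD. If they are moderately prognostic, the gain at 0.48 SD is about 6 points (61.7% to 68.1%, or 62.1% to 68.3%).

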Blueberries and other anthocyanin-rich foods have been shown to prevent a wide range of chronic diseases, yet older adults are rarely included in feeding and cohort studies. Many of the known effects of blueberries could have particular importance for older adults, but because of their unique physiological needs, it is difficult to extrapolate the effects of diet from studies completed in younger populations. This randomized parallel-design trial will examine the clinical and physiological effects of 3-months of daily whole blueberry consumption in adults ages 70+, who are independent-living residents of the senior living facility NewBridge on the Charles in Dedham, Massachusetts.

Participants will be randomly assigned to consume either whole frozen blueberries or dried dates daily for 12 weeks. We anticipate enrolling approximately 70 adults (~60% female, ~40% male). In-person follow-up will occur at Week 12 post-randomization.

Primary Outcome: Blood pressure measured by 24-hour ambulatory blood pressure monitoring and seated and standing automated office blood pressure measuring at baseline and follow-up.

Primary Aims:

- Physical function, measured by grip strength and the Short Physical Performance Battery of balance/walk/chair stands
- Falls, defined as any fall, slip, or trip in which participant loses balance and lands on the floor, ground, or at a lower level, as measured by the Study To Understand Fall Reduction and Vitamin D in You (STURDY) screening protocol
- Cognition, measured by the Cogstate Brief Battery of four core cognitive domains including processing speed, attention, visual learning, and working memory

Secondary Aims:

- Sleep, measured by the Pittsburgh Sleep Quality Index (PSQI)
- Incontinence, measured by the Questionnaire for Urinary Incontinence Diagnosis (QUID)
- Bone turnover, measured by C-terminal telopeptide of type 1 collagen
- Cardiovascular risk, measured by troponin I, total and HDL cholesterol
- Cardiac ectopy, measured by atrial premature beats detected by Holter monitor
- Liver function, measured by AST, ALT, albumin, total and direct bilirubin
- Kidney function, measured by creatinine and albuminuria
- Glucose metabolism, measured by fasting glucose and insulin, fructosamine, and free fatty acids
- Inflammation, measured by C-reactive protein and white blood cell count

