Cognitive function		X			X
Sleep, quality of life, incontinence, and dietary questionnaires		X			X

Debrief					X
---------	--	--	--	--	---

Measurements

The following sections describe the specific measurements to be collected from participants, in accordance with the above Data Collection Schedule. We have used all of the surveys and questionnaires proposed below in other studies, and all are suitable for older adults. Surveys include the PSQI, (34) the Cogstate Brief Battery, (35) the QUID, (36) the NHANES 2009-10 Dietary Screener Questionnaire (DSQ), (37) and the Health-Related Quality of Life (38). Functional measures include the SPPB and grip strength (39).

For the primary outcomes:

Blood pressure. In this trial, blood pressure will be assessed in several ways. At the BV and the FV, participants will be fitted with and instructed on a 24-hour Ambulatory Blood Pressure Monitor (ABPM). Blood pressure will be continuously monitored and recorded; average wake-time systolic blood pressure will be the primary outcome. Participants will return the ABPM for data upload the following day. At the BV and the FV, participants will undergo seated and supine-to-standing orthostatic blood pressure measurements. A&D Medical ABPMs and software will be used. Omron 907 AOBP machines will be used to measure seated and standing blood pressure.

Physical function. We will assess physical function in various ways. Participants will undergo a grip strength assessment using the average of two measurements in the dominant hand with a Jamar digital handheld dynamometer at the BV and the FV. We will measure functional limitations using the Short Physical Performance Battery (SPPB), an objective assessment developed at the NIA. The SPPB includes timed tests for usual gait speed, balance, and the ability to rise from a chair. A usual-paced 4-meter walk is timed to assess gait speed. For balance, participants are asked to maintain their feet in side-by-side, semi-tandem, and tandem positions for 10 seconds each. Finally, participants are asked to stand up and sit down five times as quickly as possible. Each test is scored from 0 to 4 using cut points from a large population-based study. The final SPPB score, which will serve as the primary functional outcome, is calculated as the sum of the three tests with a range between 0 and 12, with higher scores reflecting better physical performance. Individual components will be secondary outcomes of the trial.

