Participants that share a residence will be randomized as a household. That is to say, the second participant from the same household enrolled in the study will not be randomized, but rather automatically assigned to the study fruit that their spouse was assigned. This approach is intended to prevent cross-contamination and promote adherence and statistical plans will account for clustering if multiple household members are enrolled.

In both arms, participants are asked to avoid other anthocyanin-rich foods, including blackberry, cherry, concord grape, cranberry, currant, eggplant, plum, purple potato, red and black raspberry, red cabbage, red wine, rhubarb, and strawberry.⁽⁴⁰⁾ Participants will be provided a list of foods to avoid. They will also receive counseling and materials at the BV and throughout the study on ways to track and incorporate the assigned fruit. All participants will also be asked to maintain their 'usual' lifestyle throughout the 12-week period. This includes restricting changes to their exercise, diet, medication use, and other behaviors.

11. Safety

Safety monitoring

The study will actively monitor participant safety. One aspect of safety monitoring is to evaluate screenees to determine whether it is safe for them to participate. Key safety related eligibility criteria are the exclusion of persons with (a) an intolerance or allergy to blueberries or dates or (b) allergy to tree nuts, peanuts, soy, or milk products. The dried dates procured for the study are purchased from a supplier that also handles tree nuts, peanuts, soy, and milk products.

A second aspect is monitoring enrolled participants for safety issues potentially related to the study. Surveillance for serious adverse events and other relevant clinical events will occur by questionnaire and contact with participants. If a participant develops a medical problem, the safety of continuing or resuming the study will be ascertained by the PI and other clinical study team members.

In addition, blood pressure values at the SV, BV, and FV will be compared to the alert values based on average seated measurement. All participants with an elevated seated blood pressure measurement (SBP >180 or DBP >110 mm Hg) should be asked if they have the following symptoms: headache, vision change, chest pain, shortness of breath, or change in urine color. Study physician and/or PCP will be notified as necessary.

Table 3. Blood pressure alert values.

Issue	Action

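### Do the detectable effects of 0.68 and 0.48 SD misstate the trial's power because they ignore baseline adjustment, attrition and household pairs?

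*Protocol*

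**What the plan says.** All the power material is in section 12 of the protocol, under Power and sample size. The basis is given in one sentence: "We estimate power for our continuous endpoints, contrasting end-of-treatment values between arms", using N=70. At alpha 0.05 the detectable standardized effect is 0.68 at 80% power and 0.48 at 50% power. The second is labelled medium, and the paragraph concludes that the trial should detect most moderate-to-large effects and many medium-sized ones.

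Under Analysis plan, the same section names "linear regression models that adjust for baseline values as our primary statistical method". It then covers two contingencies. The first is "If missing data exist (e.g., due to attrition), linear mixed models" using baseline and end-of-treatment values. The second is methods for clustered data, which "will be used if multiple household members are recruited". Section 10 explains why clustering could arise: a second participant from a household is "automatically assigned to the study fruit that their spouse was assigned".

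Seventy is also the recruitment target (section 2, "We anticipate enrolling approximately 70 adults"). For blood pressure, section 7 specifies that "average wake-time systolic blood pressure will be the primary outcome".

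**The concern.** A power statement should describe the analysis that will be done. Here the primary model conditions on the baseline value, while the power figures contrast follow-up values alone. The number powered equals the number enrolled, so nothing is allowed for loss to follow-up in a population aged 70 and over. Spouses share an arm, so each couple carries less information than two unrelated people, and no design effect appears.

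If the stated 0.68 SD were materially too small for the real analysis, a null result on wake-time systolic pressure would be read as stronger evidence of no effect than it is. If it were materially too large, the trial would look weaker than it is.

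The closing sentence about medium-sized effects adds to the unease. It leans on a figure quoted at 50% power, and a reader who skips that qualifier might take it as a claim of adequate power.

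**Working it through.** **Inputs from the protocol.** 70 participants, 1:1 allocation (section 9), alpha 0.05, power 80% and 50%. Sidedness is not stated; two-sided reproduces the figures and one-sided (0.600 and 0.397 SD) does not.

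**Inputs the protocol does not give, so assumed here.** Baseline to follow-up correlation r from 0.3 to 0.7; attrition from 0 to 20%; share of participants in couples and within-couple ICC, either none, 0.25 with 0.2, or 0.50 with 0.3.

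**Step 1: the stated figures.** For a two-sample t-test with 35 per arm and 68 df, the noncentrality is d × √70 / 2 = 4.183 d.
- 80% power: d = 0.679, stated as 0.68.
- 50% power: d = 0.475, stated as 0.48.
- Power at d = 0.5: 54%.

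Both figures reproduce.

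**Step 2: add only the baseline adjustment, all 70 analysed.** The residual SD is multiplied by √(1 − r²), and one df is lost (67 df).

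| r | √(1 − r²) | Detectable at 80% | Power at 0.68 SD | Power at 0.5 SD |
|---|---|---|---|---|
| 0.3 | 0.954 | 0.648 | 84% | 58% |
| 0.5 | 0.866 | 0.588 | 90% | 66% |
| 0.7 | 0.714 | 0.485 | 98% | 82% |

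On this point alone the stated figures are conservative.

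**Step 3: add only the losses, no adjustment.**
- 10% attrition: 70 × 0.9 = 63 analysed, detectable effect 0.717 SD.
- 20% attrition: 70 × 0.8 = 56 analysed, detectable effect 0.762 SD.
- Couples: for same-arm pairs the design effect is 1 + share × ICC. With 0.25 × 0.2 it is 1.05, and the detectable effect is 0.697 SD.

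On these points alone the stated figures are optimistic.

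**Step 4: all together.** Effective N = 70 × (1 − attrition) / [design effect × (1 − r²)]; df = 70 × (1 − attrition) / design effect − 3. The larger design effect is 1 + 0.50 × 0.3 = 1.15.

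| r | No attrition, no couples | 10% attrition, design effect 1.05 | 20% attrition, design effect 1.15 |
|---|---|---|---|
| 0.3 | 0.648 | 0.702 | 0.783 |
| 0.5 | 0.588 | 0.637 | 0.710 |
| 0.7 | 0.485 | 0.525 | 0.586 |

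The first column belongs in the table because the protocol makes both attrition and household enrolment conditional. The whole range is about 0.49 to 0.78 SD, and the stated 0.68 is inside it.

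**Step 5: break-even.** The correlation at which the adjusted analysis has exactly the stated 0.68 SD is 0.38 with 10% attrition and design effect 1.05, and 0.56 with 20% and 1.15. With no attrition and no couples, any r in the assumed range beats 0.68.

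**The case for a change.** The best case for a change is that this is not a detail deferred to a statistical analysis plan. The power statement and the primary method are in the same section and describe different analyses, and the stated figures match the named model only if baseline and follow-up values are essentially uncorrelated. Calling the t-test conservative answers only the covariate; attrition and same-arm couples push the other way. Mixed models do not rescue the lost power, since with one baseline and one follow-up a participant without follow-up adds little to the week 12 contrast. The remark on medium-sized effects can be faulted without any outside assumption: 54% power at 0.5 SD is near even odds. A rewrite would cost one paragraph.

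Most of this stands as description. The figures are unadjusted, they treat all 70 as analysed and independent, and a fuller paragraph would be more informative. What does not follow is that the present paragraph misleads. It says which contrast and which N it uses. It covers the continuous endpoints collectively in SD units, and because baseline correlation can differ between endpoints, a common figure without that gain is a defensible choice. The 50% power behind the medium-effect claim is disclosed in the sentence that gives the figure, and the conclusion grades its language, with most for larger effects and many for medium ones. Many is a fair word for just over half. With baseline adjustment and all 70 analysed, power at 0.5 SD would be 66% at r = 0.5 and 82% at r = 0.7.

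A replacement range that always imposed at least 10% attrition and some couples would lean pessimistic, because it leaves out cases the protocol allows.

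**Conclusion.** No change to the plan is needed. The detectable effects are arithmetically right for the comparison the protocol says it used. They omit one gain (baseline adjustment) and two possible losses (attrition, same-arm household members). Under assumed inputs the net result runs from about 0.49 SD (r = 0.7, no attrition, no couples) to about 0.78 SD (r = 0.3, 20% attrition, design effect 1.15), with the stated 0.68 SD between them. The protocol supplies no correlation, attrition rate, share in couples or ICC, so the direction of the net error cannot be settled and the trial is not shown to be underpowered.

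The analysis already names methods for each omitted feature: baseline adjustment, mixed models for missing data and clustered-data methods for households. Rewriting the power paragraph would leave the estimate, the test, the error rate, the number recruited and the conclusions as they are. What remains is a point of labelling. A colleague citing these figures should describe them as unadjusted with 70 analysed, and should note that power at 0.5 SD on that basis is 54%.
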